# Marijuana Administration at Home

The proposed work will utilize a design that is observational and does not involve assignment by the research team. More specifically, patients who are already planning to try marijuana as a treatment for their pain will choose their own product at baseline and inform staff of their choice. The patient will then purchase the product at a dispensary. The patient will be observed before they purchase and begin using their product (Baseline Appointment), during use (Daily follow-up messages), and after 2-weeks (2-Week Appointment) of using their product ad libitum at home. After the 2-Week Appointment, we will complete Monthly follow-up surveys with the patient for 6 months to determine what additional products the patient may have tried and to collect self-report information on product use and current levels of pain.

Specifically, at the end of the Baseline Appointment, individuals will be asked to select and purchase an edible marijuana product to use ad libitum for the next 2 weeks. Colorado requires all edibles to be tested by a state lab, which allows us to have a precise measure of potency after the participants purchase their products. Importantly, the researchers who conduct the assessments as well as all the senior investigators will be blind to the participant's product choice. Participants will use their selected product at home consistent with the packaging directions, direction from their physician, or as they see fit, and will be asked not to use any other marijuana product during the 14 days before their 2-Week Appointment (with one Pre- and two Post-administration mobile assessments on the final day of the 2-week ad libitum study period). Study staff will not provide any directions regarding dosing and administration.

## Rationale for Marijuana Administration Procedure

With respect to the naturalistic aspects of the design, it is important to note that we carefully considered alternative designs. The federally sourced marijuana supplied through NIDA does not currently offer any edible marijuana products (www.drugabuse.gov), although these are widely available through Colorado dispensaries and used in great numbers by Colorado residents and patients to provide relief from chronic pain. Thus, we are not able to acquire marijuana edibles via NIDA-supply and administer them directly to participants via a tightly controlled randomized clinical trial. Given the dearth of data available on why so many people are turning to marijuana as a treatment for pain and on the effects of marijuana edibles more broadly, we developed our design that naturalistically reflects common routes and methods of administration of marijuana in medical patients, particularly in states with legalized marijuana. Because the long-term goal of this work is to better understand the effect of different levels of

Page 8 of 34

cannabinoids in edible marijuana in pain patients, as they are used real world, we decided that it was critically important to emphasize external validity. The disadvantage of our observational design is that we do not have direct control over the choice of product or the dosing and administration of the marijuana. To address this limitation, both in our pilot study and in this application, we rely on blood quantitation of cannabinoids to determine the level of THC and CBD in each subject. Thus, regardless of which product the participant uses or how much of the edible is consumed, we have an objective measure of circulating THC and CBD for each subject, which is the sine qua non of pharmacological research. This aspect is also critical for our analytic approach, which is the analysis of THC and CBD levels in blood

Finally, it is worth noting that being a major research university in a community that was the first in the United States to legalize recreational marijuana use gives us the unprecedented opportunity to be at the forefront of innovative research to build the knowledge base on marijuana harm reduction. As such, we have worked very closely with the legal team at the University of Colorado to develop our methodological approach so that it does not violate any federal laws, such as the Controlled Substances Act and Drug Free Schools Act.

# **Blood Analyses of Inflammation**

As noted in the background and in our description of our preliminary studies, we expect that CBD and THC will reduce biomarkers related to inflammation during the course of the study. Blood samples drawn at each assessment will be assayed for IFNg, IL-1a, IL-1b, IL-6, IL-2, IL-4, IL-8, IL-10, IL-12, and TNF. Previous studies in animals  and humans, as well as our own preliminary data, suggest that cytokine activation is associated with the pathophysiology of pain. This is the same assay used in our preliminary studies. To that end, 40 mL of whole blood will be drawn at each assessment point. We will collect 40 ml of blood at each blood draw. We will use 24 ml of blood to perform the inflammatory analysis, and 16 ml of blood for cannabinoid analysis. There will be four blood draws total, with one during the 1st Appointment (Baseline) and three (each separated by an hour) during the 2nd Appointment (2-Week Mobile Van). We will measure changes in cannabinoid and inflammatory levels after the long (2-week pre) and short/acute (1 and 2hour post) time course of edible consumption.

# **Power Analysis and Sample Size Requirements**

Sample size was selected to permit analysis of the primary research questions at two-tailed alpha of .05 and power level of .80. Estimates of effect size follow Cohen and were conducted in G\*Power 3. We will rely on cannabinoid blood levels (e.g. THC and CBD and their relevant metabolites) as continuous independent variables to predict study outcomes. Thus, we will be testing regression coefficients in the context of a multivariate model with, in the simplest case, three predictors (THC level, CBD level, and the THCXCBD interaction). With a sample of 246 participants, we will be able to detect effects as small as  $f^2 = .04$  with power = .88. This is critical particularly for hypotheses as in each case we predict interaction effects of THD and CBD in blood. It is well known that tests of interactions in non-experimental, observational designs are notoriously small, and thus it is critical that we are adequately powered to detect small effects.

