We propose to examine the effects of cannabinoids in edible form on pain relief, inflammation, and cognitive dysfunction in chronic low back pain patients who choose to use marijuana in the context of a short-term (2 weeks) mechanistic study using a patient-oriented, observational design and a Mobile pharmacology and phlebotomy lab that solves many of the logistical problems with marijuana research. Our global hypothesis is that our observations of self-report and objective measures of the effects of marijuana edible products by pain patients who choose to use these products will vary as a function of the levels of THC to CBD in their blood. Further, we hypothesize that cognitive impacts observed will differ by the THC/CBD levels in blood. To that end, we will measure the association of pain, inflammation, and cognitive impairment with the levels of THC and CBD in the blood of pain patients who wish to use edible cannabis to treat their pain. This approach is ecologically valid and timely given that edibles of various cannabinoid ratios are widely used by patients in state legalized markets, yet absolutely no research has been done on these products. Edibles generally have either THC-only, CBDonly, or include both THC and CBD. Recent data, including our pilot work, suggest that THC and CBD together produce unique effects on pain, inflammation, and cognition. We will use a patient-oriented, observational design, in which chronic low back pain patients who self-initiate the use of a marijuana edible to manage their pain are observed over their 2-Week study period while using a product of their choosing. THC and CBD blood levels will be tested in relation to all outcomes.

Page 2 of 34

**Aim 1.** To investigate the mechanisms that may underlie the widespread use of marijuana among pain patients in a 2-week observational study of ad-libitum use, we will observe whether there is an association between cannabinoid levels in blood and measures of self-reported pain.

Hypothesis 1. Based on numerous studies that suggest CBD and THC may work together to produce the analgesic effects of marijuana, we hypothesize that higher blood levels of both THC and CBD will have the strongest association with lower levels of **pain interference** after 2 weeks.

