Hypothesis 2. Given the role of elevated **inflammatory markers** as an underlying mechanism involved in chronic pain, we predict that THC and CBD blood levels will additively be most strongly associated with lower levels of four circulating cytokines (TNFα, IL-6, IL-8, IL-1B) after 2 weeks.

**Aim 2.** To understand the relationship of self-directed edible cannabis-use to cognitive function in individuals with chronic low back pain, we will observe the association between cannabinoid levels in blood and measures of cognitive function.

Hypothesis 3. Based on prior research and our preliminary data, we predict an interactive relationship of blood levels of THC and CBD to cognitive impairment, such that at lower levels of CBD in blood, THC blood levels will be dose-dependently associated with **poorer verbal recall and selective attention** after 2 weeks of *ad libitum* use, whereas at higher levels of CBD in blood, the relationship of THC in blood to cognitive impairment will be attenuated.

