# **Specific Aim 1:**

# **Hypothesis 1**

**Objective 1:** We will observe levels of pain in individuals with chronic low back pain who engage in 2 weeks of *ad libitum* use of marijuana edible product of their choice with various cannabinoid content. *Hypothesis 1* predicts that observed THC and CBD blood levels will impact lower levels of low back pain interference after 2 weeks, compared to THC or CBD blood levels considered in isolation.

**Primary endpoint/analysis**: The Roland Morris Disability Questionnaire (RMDQ) has been used in studies of low back pain and asks participants about how their experience of low back pain interfered with 24 daily activities in the past two weeks; total score ranges from 0-24. Using the total RMDQ score, we will test pain interference using two time points – Baseline (prior to taking any cannabis) and 2-Week Pre-administration (after 2 weeks of product use but immediately before last edible use in the 2-Week study period). We will test a ordinary least squares (OLS) regression model in which blood levels of CBD, THC, and the CBDxTHC interaction are used to predict 2-Week pre-administration pain interference controlling for Baseline pain interference. Note that our participants are naïve to recent cannabis use at Baseline (per our eligibility criteria) so it is not necessary to control for Baseline levels of cannabinoids. Thus we are testing the effect of blood levels of cannabinoids on experience of recent pain interference. We predict that higher levels of THC and CBD will be associated with less pain interference.

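### The sample-size section says a THC×CBD interaction is predicted for every hypothesis, but H2 is called both additive and interactive and H1 is ambiguous; no test is named to decide either, and no success rule covers the four cytokines or two cognitive co-primaries

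*Combined protocol and SAP*

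**What the plan says.** The section Power Analysis and Sample Size Requirements sets the error rate and target: "Sample size was selected to permit analysis of the primary research questions at two-tailed alpha of .05 and power level of .80". It describes the test in general terms: "we will be testing regression coefficients in the context of a multivariate model with, in the simplest case, three predictors". These are THC, CBD and their product. With 246 participants and f² = .04 it reports power of .88. It then explains why small effects matter: "This is critical particularly for hypotheses as in each case we predict interaction effects of THD and CBD in blood".

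The hypotheses read differently:

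- **H1, pain interference.** Objectives: "higher blood levels of both THC and CBD will have the strongest association with lower levels of" pain interference. The SAP objective sets the joint effect against a comparator: "compared to THC or CBD blood levels considered in isolation". The primary prediction is "We predict that higher levels of THC and CBD will be associated with less pain interference". An explicit interaction is predicted only for the acute secondary pain analysis.
- **H2, cytokines.** Objectives: "we predict that THC and CBD blood levels will additively be most strongly associated with lower levels of four circulating cytokines". The SAP objective also says additive. The primary analysis under the same heading then predicts interactive effects, with the lowest inflammation in participants high on both cannabinoids. Four cytokines are primary, each analysed individually.
- **H3, cognition.** Objectives: "we predict an interactive relationship of blood levels of THC and CBD to cognitive impairment". The SAP primary analysis agrees. The Flanker score and delayed verbal recall are called co-primary.

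All three primary analyses use the same OLS model: THC, CBD and the product, controlling for the baseline outcome. The plan gives no testing order, no rule on whether one or all outcomes must succeed, and no multiplicity adjustment.

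**The concern.** An additive claim and an interactive claim are decided by different tests of the same fitted model. If the cannabinoids act additively, the product term carries no signal and its test rejects only at about its alpha, while a joint test of the two main effects may reject with high power. For H2 the plan makes both claims, and for H1 it leaves the choice open. Three coefficients will be available per outcome, and the plan does not say which one confirms the hypothesis.

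The second gap compounds the first. H2 has four primary outcomes and H3 has two. Whether one success or all are needed determines whether the false-positive rate is inflated or the power reduced. The reported .88 describes neither case.

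**Working it through.** **Inputs.** From the power section: N = 246, f² = .04, two-tailed alpha .05, target power .80, stated power .88. From the SAP: four predictors in each primary model (baseline, THC, CBD, product), four cytokines, two cognitive outcomes. The documents give no correlations between outcomes and no cannabinoid levels, so both are assumptions below and are shown as ranges.

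**1. Reproduce the plan's figure.** Noncentral F with λ = f² × N = .04 × 246 = 9.84 and denominator df = 246 − 4 − 1 = 241.

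- One coefficient (1 df): power .878, which matches .88. Using three predictors instead of four gives the same value.
- Two main effects jointly (2 df): .804.
- All three terms (3 df): .746.

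So .88 is the power for one coefficient, on one outcome, at unadjusted .05.

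**2. Effect of the choice of test under an additive truth.**

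- Product coefficient: rejects at about .05 (.045–.051 in simulated OLS fits).
- 2-df THC+CBD test: .80 if the total f² is .04 (λ = 9.84), and .98 if each cannabinoid contributes .04 (total .08, λ = .08 × 246 = 19.68).
- If only one cannabinoid is active at f² = .04, the 2-df test still rejects .80 of the time, whereas a rule requiring both coefficients rejects .02. Only the both-coefficients rule therefore addresses a claim set against either cannabinoid in isolation.

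**3. Effect of the success rule.** With independent tests, any-one error is 1 − .95^k and all-rule power is .878^k:

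- k = 4: 1 − .95⁴ = .185; .878⁴ = .59.
- k = 2: 1 − .95² = .0975; .878² = .77.

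With equicorrelated normal test statistics:

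| Correlation (assumed) | Any-one error, 4 cytokines | Any-one error, 2 cognitive | All-rule power, 4 | All-rule power, 2 |
|---|---|---|---|---|
| 0 | .185 | .098 | .59 | .77 |
| .5 | .156 | .090 | .70 | .80 |
| .8 | .114 | .078 | .77 | .83 |
| .9 | .094 | .071 | .81 | .84 |

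**4. Power if alpha is split.** One coefficient, f² = .04: .810 at .05/2 = .025 and .732 at .05/4 = .0125. These are the first Holm steps. Full Holm power per cytokine is .73 if only one is truly associated and .80–.84 if all four are. Per cognitive score it is .81 if one is and .85–.87 if both are.

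**5. Why centring matters for a main-effect test.** In a model with the product, the THC coefficient is the slope at CBD = 0, and the CBD coefficient is the slope at THC = 0. Subtracting means before forming the product moves those reference points and changes both coefficients and their joint test. The product coefficient and its test do not change. Simulation: N = 246, a baseline covariate, assumed lognormal levels (log SD .5 to 1.0, THC–CBD correlation 0 to .3), additive truth of 0.2 residual SD per SD of each cannabinoid.

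- 2-df test: .92–.99 centred, .25–.61 uncentred.
- Both-coefficients rule: .52–.74 centred. With idealised t statistics, each at f² = .04, it is .76–.77.

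**The case against.** - **H1 can be read as interactive.** The Objectives suggest the cannabinoids work together, the SAP contrasts their joint effect with either alone, the model holds the product, and the power section says interaction in each case. This stands: H1 is ambiguous, not contradictory. A reader might infer that all the hypotheses conflict with the power section, but only H2 does.
- **Co-primary often means both must be met, which needs no alpha split.** That may be the intent for H3. The plan does not define the term and does not apply it to the cytokines, where the stress on individual markers could equally mean separate reporting.
- **The study is observational and mechanistic.** Formal error control within families is therefore one defensible choice, not an obligation. Even so, the plan sets primary endpoints, an alpha, a power target and directional predictions, so it should say what confirms them.
- **Freedom is already limited.** Hypothesis tests wait for data lock, and directions are pre-stated. This helps. Counting only results in the predicted direction, four independent cytokines still give 1 − .975⁴ = .096 against a nominal .025. Neither safeguard names the test or the rule.
- **The .05 versus .98 contrast is favourable.** It uses a total f² of .08. At the plan's own .04 the joint test has .80, which is still far from .05.

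**Conclusion.** The point holds and should be fixed before data lock. H2 carries two incompatible statements, H1's deciding test is open, and six primary outcomes sit in two families with no success rule.

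Three stronger readings are not supported:

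- **That the power calculation is wrong.** The .88 reproduces; it is narrower than the hypotheses it is used for.
- **That error is inflated.** This follows only if any one success suffices, which the plan does not say. If all must succeed, error is not inflated and the cost is power.
- **That an all-rule must leave the cytokines below the .80 target.** This holds for the correlations shown up to .8 but not at .9, where power is .81.

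The figures rest on N = 246 and f² = .04 per tested coefficient unless stated, on assumed correlations between outcomes, and, for the centring and both-coefficients results, on assumed cannabinoid distributions.

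**What to change.** Before data lock:

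1. **Reconcile the power section with H1 and H2, and name one deciding test per outcome.** Use the THC×CBD coefficient for any hypothesis kept as interactive, as H3 is. For any kept as additive, use a 2-df THC+CBD test, or require both coefficients if the claim remains a comparison with either cannabinoid in isolation. For either additive option, it is a requirement to mean-centre the (transformed) levels before forming the product or to run the test in a model without the product.
2. **State whether one or all outcomes must succeed.** If one suffices, apply Holm within the four cytokines and, separately, within the two cognitive scores. If all must succeed, no alpha split is needed. H1 stays at .05.
3. **Say that .88 applies to one coefficient on one outcome, and report power for the chosen rule.** For Holm, report .81 at .025 and .73 at .0125 (first steps). For an all-rule, report the tabulated values with their assumed correlations. For a 2-df test at .05, report .80 if total f² = .04 and .98 if it is .08. For both coefficients at .05, report about .5 to .77, depending on the assumed skew and correlation of the levels.

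This costs SAP wording only, with no new data or participants. The downside is less favourable stated power, mainly for the cytokines and for the both-coefficients option.

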# The impact of attrition

It is anticipated that some attrition will occur. Based on our current pilot study and previous marijuana studies, we anticipate a 10-15% attrition rate between the Baseline and the 2-Week Appointment. Though we have not experienced differential attrition by condition, and do not anticipate attrition by edible selection, we assume an approximate 85% retention rate over the course of the primary data collection. To adjust for this attrition rate, we will recruit n≈289 participants.

# Statistical Analysis Plan

Analyses will be conducted primarily on the SAS system for Windows Version 9.4 which includes capabilities to test multilevel models that appropriately model both normally and non-normally distributed data as well as missing data. The distributional properties of continuously scaled variables

will be examined for skewness and kurtosis to determine appropriate analytic techniques or normalizing transformations prior to the primary analyses.

# **Specific Aim 1:**

# **Hypothesis 1**

**Objective 1:** We will observe levels of pain in individuals with chronic low back pain who engage in 2 weeks of *ad libitum* use of marijuana edible product of their choice with various cannabinoid content. *Hypothesis 1* predicts that observed THC and CBD blood levels will impact lower levels of low back pain interference after 2 weeks, compared to THC or CBD blood levels considered in isolation.

**Primary endpoint/analysis**: The Roland Morris Disability Questionnaire (RMDQ) has been used in studies of low back pain and asks participants about how their experience of low back pain interfered with 24 daily activities in the past two weeks; total score ranges from 0-24. Using the total RMDQ score, we will test pain interference using two time points – Baseline (prior to taking any cannabis) and 2-Week Pre-administration (after 2 weeks of product use but immediately before last edible use in the 2-Week study period). We will test a ordinary least squares (OLS) regression model in which blood levels of CBD, THC, and the CBDxTHC interaction are used to predict 2-Week pre-administration pain interference controlling for Baseline pain interference. Note that our participants are naïve to recent cannabis use at Baseline (per our eligibility criteria) so it is not necessary to control for Baseline levels of cannabinoids. Thus we are testing the effect of blood levels of cannabinoids on experience of recent pain interference. We predict that higher levels of THC and CBD will be associated with less pain interference.

Secondary endpoint/analysis: Using the "current pain" version of the Pain Intensity scale (i.e., "Rate your pain level right now." on a scale from 0-10) we will test acute effects of cannabinoids on pain at the 2-Week Appointment, using three time points: a) Pre administration (before the last edible use), b) Post-1h administration (1 hour after the last edible use), and c) Post 2h administration (2 hours after the last edible use) of the 2-week ad libitum study period. We will test a RCR model in which changes in blood levels of CBD, THC, the CBD x THC interaction time (pre administration, 1-hour post-administration, and 2 hours post administration) and all possible interactions are used to predict pain. All independent variables in this analysis are within-subjects as they occur over time. Thus, we are testing the effect of changes in blood levels of cannabinoids on changes in acute pain. We predict that greater increases in THC and CBD acutely will be associated with greater decreases in pain, and that there will be interactive effects such that those participants with the greatest increases in both THC and CBD will experience the greatest decreases in acute pain.

Other secondary endpoints will be analyzed using the same modeling structure described above as appropriate and include: Pre-administration Pain intensity over the two weeks prior to the 2-Week Appointment (average of current, worst, and average back pain over the prior two weeks); Pre-administration Depression, Anxiety, and Stress subscales of the Depression Anxiety Stress Scale (DASS) over the prior two weeks; the Patient Global Impression of Change scale which asks participants to rate their improvement in pain over the prior two weeks on a 7-point scale (completely gone, much better, somewhat better, a little better, about the same, a little worse, and much worse).

